1. BACKGROUND

The need for treatment and prevention of overdose is a national priority according to the Centers for Disease Control (CDC) which lists expanding access to addiction treatment services as an essential component in the response to the opioid overdose epidemic.¹ Less than 10% of justice-involved individuals are able to access behavioral health services on any given day regardless of setting (i.e. jail, probation, etc.),²⁻⁵ however the Criminal Justice System (CJS) has some constitutional driven needs to provide behavioral health care (i.e., mental health and substance use) to the largest concentration of U.S. adults with behavioral health needs. Nearly 11 million individuals pass through local jails each year,^{6,7} 5 million individuals are on parole or probation,⁸ and 1.5 million are in state and federal prisons.⁶ Among CJ populations, the rate of past-year substance use disorder (SUD) (66%),^{1,9-19} lifetime opioid use (15%),¹ and pain medication dependence (11%)¹ are dramatically elevated compared to the non-criminal justice population, resulting in overdose,¹² suicide,²⁰⁻²² disabilities and physical disorders,²³⁻²⁵ homelessness,²⁶ and death.^{27,28}

While pharmacotherapy holds great promise, medications are underutilized in SUD treatment, both in and out of the CJS.^{29,30} Of the three most common medications for opioid use disorders (MOUDS)--methadone, injectable naltrexone, and buprenorphine-- all possess evidence that they increase retention in treatment, reduce self-reported use of opioids, and reduce criminal activity and mortality.³ Approximately 80% of those with opioid use disorders (OUD) do not receive appropriate treatment.^{4,5} Utilization of MOUD among justice populations is even lower³¹ with justice referred patients being one-tenth as likely to receive agonist MOUD as other patients.³² Addressing justice system actors' attitudes is important for expanding use of medications³³ and for guiding implementation.

The CJS offers an opportune setting to disseminate and implement evidence-based practices (EBPs) because of the gap between evidence and practice, potential return on investment in order to reduce fatalities, reduced burden on the health and criminal justice (CJ) agencies, and improved quality of life. The pressing question is how best to facilitate dissemination, adoption, implementation, and sustainment of EBPs for CJ populations.

2. STUDY SYNOPSIS

The current timeframe from research lab to practice is 17 years, with only 14% of clinicians reporting use of evidence-informed knowledge in their clinical practice.³⁴ Complexities of the CJ or health systems coupled with interagency features present challenges to the effective dissemination, adoption, implementation, and sustainment of evidence-based practices. Coaching is a favored implementation strategy, yet coaching dosage and mediums have not been adequately tested or assessed in CJ settings. Scaling up in CJS, particularly MOUD utilization, presents a challenge given staffing resources available, acceptance of addiction treatment, and historical preference for behavioral therapy-based treatment practices that often do not include use of MOUD. In this trial, we will test two implementation interventions being applied to MOUD dissemination and implementation in justice settings for justice-involved populations: NIATx Coaching and the Extension for Community Healthcare Outcomes

(ECHO) model. NIATx Coaches provide expertise in MOUD implementation and organizational change to help treatment organizations and staff make, sustain, and spread MOUD. The ECHO platform focuses only on the provider side by connecting the primary care provider with expert MOUD prescribers to promote high-quality MOUD practices. This will be the first trial that assesses the comparative effectiveness of these approaches overall, and in justice settings.

The trial will be conducted with a combination of 48 jails and community-based organizations that treat individuals with OUDs post-incarceration. Sites will be randomly assigned to one of four study arms, with 12 sites in each arm: High-Dose Coaching/ECHO, Low-Dose Coaching/ECHO, High-Dose Coaching/No ECHO, and Low-Dose Coaching/No ECHO. The intervention period will be over a 12-month span with an additional 12-months for sustainability.

3. STUDY OBJECTIVES

The specific aim of this study is to compare High-Dose NIATx Coaching/ECHO, Low-Dose NIATx Coaching/ECHO, High-Dose NIATx Coaching/No ECHO, and Low-Dose NIATx Coaching/No ECHO. Impact will be measured using the RE-AIM framework:

- *Reach* (primary aim) measured as the percent of eligible justice involved patients who 1) are initiated onto any MOUD (buprenorphine, extended-release injectable naltrexone, or methadone), and 2) engaged with MOUD use.
- *Effectiveness* measured in terms of impact of MOUD involvement on re-arrest rates.
- *Adoption* measured as the percent of eligible clinicians in jail and/or community providers who use MOUD.
- *Implementation* measured by an organizational readiness for MOUD implementation over time and intervention fidelity scale (*for NIATx and ECHO*).
- *Maintenance* measured as the likelihood of organizations sustaining provision of MOUD utilization (organizational sustainability scores at 12 and 24 months of intervention) and we will continue to collect Reach, Effectiveness, and Implementation measures during the maintenance phase (Ms 12-24).

Study Coordination

The UW-Madison Center for Health Enhancement Systems Studies (CHESS) and George Mason University Center for Advancing Correctional Excellence! are the coordinating sites for this study. George Mason holds the grant award for the larger study this research is embedded in. The UW site will oversee all recruitment and study implementation activities which includes:

- developing organizational site-specific recruitment and data collection processes that meet study objectives;
- training staff on protocol procedures prior to start of recruitment and continuous monitoring to assure compliance with the protocol and human subjects regulation;

- communicating with clinic site staff as needed via conference calls to monitor progress, inform of protocol changes/distribute new version of protocol, and address unanticipated issues or challenges;
- manage all study data;
- oversee analysis; and
- oversee publications and presentations.

4. SELECTION OF SUBJECTS

This study will engage jails and post-incarceration community-based organizations serving justice involved persons including correctional and health staff and medical teams at those sites/organizations.

Organizations: Up to twelve (12) jails and community-based organizations from around the country, eighteen (18) jails and community-based organizations in Wisconsin, and eighteen (18) jails and community-based organizations in Virginia, with a total of forty-eight (48) sites will be recruited for this study.

Participating sites will receive \$1,000 in Year 1 and again in Year 2 for participating in the study and for submitting organizational and staff data. The funds will be used to pay for study data and/or study material.

Sites to be approached for recruitment will be: sites that have expressed interest in the grant, organizational sites that provide post incarceration addiction treatment services, and jails that provide addiction treatment services within the jail. Once sites have been identified, they will be asked to sign an IRB approved Information Sheet (Memorandum of Understanding) to indicate their understanding of the study protocol and willingness to participate in the study.

Pre-Requisites for Site Participation:

- Have an interest in embedding or increasing the use of MOUD within their site.
- Have the funds to pay for medications for the duration of the study (24 months); whether it be from grants, insurance or private pay.
- Sites agree to implement or continue to use at least one medication, although they will be encouraged to offer more than one medication.
- Have leadership support at all levels.
- Sign a Memorandum of Understanding (MOU) or Information Sheet.
- Agree to provide data described in the MOU or Information Sheet.

Executive Sponsor, Change Leader & Team: Each site will be asked to identify an Executive Sponsor to represent their respective site. This individual will be in a leadership role such as Director, CEO, Sheriff, etc. The Executive Sponsor will be responsible for identifying a 'Change Leader' or 'site liaison' (someone in a management role), willing to coordinate the study elements. It is then up to the Executive Sponsor and Change Leader to identify up to 7 staff members that will be a part of the 'Change Team' in the jail setting. Members of the Change

Team for purposes of community linkage should include CJ staff (jail or probation), health provider representative, medical provider/prescriber (i.e. nurse, physician, etc.) to ensure that the team has reach to various pertinent audiences. Additional members on the Change Team can hold a variety of positions including counselor, nurse, social worker, case manager, etc. Change teams will also be present in the post incarceration community-based provider jail SUD partner sites and will also include variety of positions including counselor, physician, nurse, social worker, case manager, etc. Once participating staff is identified by role in the jail and post-incarceration CB provider sites, recruited staff will be emailed invitations to complete organizational/staff surveys and/or a phone interview along with a study consent form. Any staff member may formally decline to participate during the training portion of the study or any time thereafter.

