5. REGISTRATION PROCEDURES

Organizational and Staff Recruitment

Organizational Surveys: The Executive Sponsor (or their designee) will complete the organizational surveys and may be asked to complete a short qualitative phone interview.

Staff Survey: The staff surveys will be completed by staff that are a part of the Change Team.

Physician Survey: The Physician Survey will be completed by physicians/prescribers working at the sites.

The Executive Sponsor will not have access to the survey data nor will they receive any data feedback or summaries from the surveys. The IRB approved consent form will describe that completing the staff or organizational survey infers their consent. For those who do not complete the survey, the survey will not be recorded and no record of the person not wanting to participate will be made. The consent form will be the first portion of the on-line survey to be administered through REDCap.

All surveys will be accessed through REDCap, a secure web-based platform, licensed by University of Wisconsin, that is used for building and managing online databases and surveys.

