The designated Executive Sponsor or the Change Leader at each site will manage staff member recruitment to construct a change team of up to a seven (7) member Change Team. Up to two of the team members will be physicians. Each member of the change team as well as the change leader will be asked to complete staff surveys at baseline, 12m, and 24ms for a total of 8 "staff" surveys per site. Information on the implementation process will be gathered from site staff members during surveys and interviews.

The full Staff Survey including Organizational Readiness for Implementing Change (ORIC), Organizational Climate-Stress, Attitudes toward MOUD and Program Sustainability, will be administered three times during the study (baseline, 12m, 24m). Each survey is expected to take approximately 20 minutes or less to complete. Staff completing the surveys will receive consent documents when they are sent the survey link via REDCap. To increase survey

completion rates for the Staff Surveys, the research team at UW will conduct follow-up phone calls and e-mails with the Change Leaders at Week 1 of post-survey distribution to assure the survey receipt, then at Weeks 4 and 12-post survey distribution if surveys are not complete. Each survey cycle, at months listed above, will include up to 384 people per cycle. The 384 staff will include up to 8 participants from the 48 sites and will include the Change Leader (supervisor/member of the leadership staff), and up to 7 team members part of the Change Team (CJ staff, prescribers, clinicians, nurses, counselors, social workers, etc). Since many of the same staff will likely complete surveys in successive cycles, 536 unique staff are expected for survey completion across all three cycles. The 536 unique people projected assumes 20% or 76 new people per round occurs post-intervention and post sustainability round. There will be a total of 1,152 surveys.

Physician Surveys & Data:

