Physician Satisfaction with MOUD	Modified Physician Worklife Survey	
 • Physician Survey 
 ○ Baseline, 12m, 24m
Implementation		
Organizational Readiness for MOUD	ORIC ³⁹	
 • Organizational Survey 
 ○ Baseline, 12m, 24m
Organizational Climate: Stress	TCU SOF ⁴¹	
 • Staff Survey 
 ○ Baseline, 12m, 24m
Maintenance		
Likelihood of MOUD sustainability	Program Sustainability Assessment Tool ⁴⁰	
 • Staff Survey 
 ○ Baseline, 12m, 24m
NIATx Fidelity & ECHO Fidelity	Organization (using a scale designed for this study)	
 • Organizational Survey 
 ○ Baseline, 12m, 24m

Qualitative Interviews

Qualitative data will be gathered from organizational staff at two points; pre-intervention (baseline) and post-intervention (12 months).

Baseline qualitative phone interviews will be completed with leadership staff at 24 randomly selected sites, six sites within each study arm. Interviews will last approximately 30-45 minutes in length and will be conducted with up to two people at each site. The interviews will be audio-taped (with staff participant permission), but the staff person's identity will be protected and in no way be linked to the results. Interviews will be semi-structured and gather information that is not included within the organizational surveys that will be completed throughout the study. This includes information about site structure and process, culture surrounding justice-involved clients, motivation for serving OUD population and approaches to organizational change. Examples of open-ended questions that will be asked;

1. Please walk me through how a justice-involved client comes to your service?
2. Are your justice-involved clients integrated into your general clientele?
3. Please tell me about the last time your organization made a change to its processes?

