8. MEASUREMENT OF EFFECT

All scales used in this study, except for the Fidelity scales developed for this study, have good tested psychometric properties with similar populations. Listed below are the factors to be measured and measurement instruments with references to validation studies.

Descriptive Statistics - Organizational traits such as admission and rural v. urban will be obtained via Organizational Survey and database. Client traits such as age, gender, ethnicity, treatment offered and CJ status will also be obtained at three points during the study via the Organizational Survey and database. Staff traits such as gender, ethnicity, and certification or education level will be obtained via the Organizational Survey at three points.

REACH - The percent of patients initiated on MOUD and length of engagement will be obtained through monthly spreadsheet data completed by organizational staff or state databases.

Adoption – The percent of prescribers using MOUD will be collected through the Organizational survey at 3 points during the study. The organizations readiness for MOUD will be collected using the Organizational Readiness for Implementing Change (ORIC) scale and the Organizational Climate: Stress measure will be collected at two points in the study.

Effectiveness – Re-arrest rates will be obtained through state police databases on a yearly basis.

Maintenance –The organizational survey, which will be administered at three points during the study, will assess the likelihood of MOUD sustainability. The Physician Survey will be completed by physicians at 3 points during the study.

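### Staff Survey respondents are picked by site leaders, with no rule that they be named before the arm is disclosed, so High- versus Low-Dose differences in staff-reported scores could partly reflect who was chosen

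*Combined protocol and SAP*

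**What the plan says.** **Who chooses and who answers.** Section 4 states "It is then up to the Executive Sponsor and Change Leader to identify up to 7 staff members", and section 6 (Staff Surveys & Data) repeats the arrangement: "The designated Executive Sponsor or the Change Leader at each site will manage staff member recruitment to construct a change team". Roles that should be represented are listed, but there is no rule for choosing individuals. Section 5 then limits the respondents to that group: "The staff surveys will be completed by staff that are a part of the Change Team". Section 6 adds the Change Leader, giving up to 8 per site.

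**What they report.** Section 6 describes the instrument as "The full Staff Survey including Organizational Readiness for Implementing Change (ORIC), Organizational Climate-Stress, Attitudes toward MOUD and Program Sustainability". Other places disagree on two of these scores:
- ORIC: the Implementation rows of Table 2 assign it to the Organizational Survey, while the organizational-traits row of the same table gives staff as the source of readiness.
- Sustainability: Table 2 assigns it to the Staff Survey, but section 8 says "The organizational survey, which will be administered at three points during the study, will assess the likelihood of MOUD sustainability".

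The Executive Sponsor or a designee completes the Organizational Survey.

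**Timing.** No section says that the team is named before randomization or before the site learns its arm. Arms exist at baseline: "Baseline qualitative phone interviews will be completed with leadership staff at 24 randomly selected sites, six sites within each study arm". Figure 1 has the team trained at the site visit or the introductory call, a step that differs by coaching dose.

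**Turnover.** Section 6 says "The 536 unique people projected assumes 20% or 76 new people per round occurs post-intervention and post sustainability round". It gives no rule for choosing replacements.

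**Analysis.** Section 10 (Intervention and Sustainability) specifies random effects for programs, cross-sectional models at each time point, and growth curves with intervention-by-time terms. It has no term for the respondent and no distinction between continuing and new respondents.

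**The concern.** In a cluster trial, randomization balances the sites. It balances the people measured within them only if those people are identified independently of the arm. Here leaders may pick the team once they know what it will be asked to do, and the request differs by dose. High-Dose teams have a four-hour site visit and 11 monthly calls; Low-Dose teams have a webinar and three calls. A leader filling the heavier role might choose keener staff, or those with more time. Replacements join after baseline, when arms are already assigned.

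The scores are read as properties of the organization: its readiness, its stress climate and the likelihood that it will sustain MOUD. A change in who answers would then be read as a change in the organization. ORIC, Climate-Stress and Program Sustainability are also listed mediators in section 10, so the same distortion could enter the mediation analysis.

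**Working it through.** **1. The plan's own counts.** Section 6 says "The 384 staff will include up to 8 participants from the 48 sites".
- Per cycle: 48 × 8 = 384.
- Unique staff: 384 + 2 × 76 = 536, as stated (537.6 with an unrounded 20%).
- Surveys: 3 × 384 = 1,152, as stated.

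**2. Share of respondents not on the baseline team.**
- Month 12: 76/384 = 20%.
- Month 24, leavers drawn at random: 1 − (308/384)² = 36%.
- Month 24, all leavers original members: 152/384 = 40%.

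If the same posts turned over twice, the month-24 share would fall towards the month-12 figure of 20%.

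**3. Precision of a High- versus Low-Dose comparison of a staff score.** Inputs: 48 sites (24 per dose level), 8 respondents each, two-sided alpha 0.05. The ICC of 0.10 is the value section 10 gives for patient outcomes; using it for staff scores is an assumption.
- Site-mean variance: 0.10 + 0.90/8 = 0.2125 (in SD² units).
- SE of the difference: √(0.2125 × 4/48) = 0.133 SD.
- Difference detectable with 80% power: 2.80 × 0.133 = 0.37 SD.

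**4. Effect of differential replacement with no true effect.** Let newcomers in one dose level score g SD higher because of who was chosen, and let everyone else be comparable. The false difference is g × share. The type I error is the probability that |Z| exceeds 1.96 when Z has mean (false difference)/0.133. The documents give no value for g, so a range is shown.

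| g (assumed) | Month 12: false difference, type I error | Month 24: false difference, type I error |
|---|---|---|
| 0.25 SD | 0.05 SD, 7% | 0.09–0.10 SD, 10%–12% |
| 0.5 SD | 0.10 SD, 11%–12% | 0.18–0.20 SD, 27%–32% |
| 0.8 SD | 0.16 SD, 22% | 0.29–0.32 SD, 57%–66% |

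At g = 0.5, an ICC between 0.05 and 0.20 gives a month-24 type I error of 20% to 39%. With the 42 sites expected after attrition and ICC 0.10, it is 24% to 29%.

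These rates are for a cross-sectional comparison. In the growth-curve interaction, differential replacement shifts the estimate in the same way, but the rejection rate also depends on the within-site correlation over time, which the plan does not give.

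**5. A difference present from the start.** If the whole team in one dose level differed by a constant 0.25 SD, the cross-sectional test would reject about 47% of the time (0.25/0.133 = 1.88). The intervention-by-time terms would net that constant out.

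**6. Precision if only the baseline roster is analysed.** The roster would be 308 people at month 12 and 232 to 247 at month 24 (384 − 152; 384 × 0.643).
- Month 24, 232 people (4.83 per site): variance 0.10 + 0.90/4.83 = 0.286; SE = √(0.286 × 4/48) = 0.154; detectable difference 0.43 SD.
- Month 24, 247 people (5.15 per site): variance 0.275; SE 0.151; detectable difference 0.42 SD.

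**The case against.** **The documents do not show that leaders knew their arm.** This stands. Drawing interview sites within arm shows that the study team had assigned arms. It does not show that sites had been told. A reader might infer that teams were picked in knowledge of the arm, but the plan only fails to exclude it. The gap matters more for replacements, who join after baseline whatever happened at the start.

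**The Change Team is the group that coaching targets.** This also stands in part. If dose changes who serves, that can be counted as part of the strategy's effect. It does not justify reading the result as a change in the organization without being able to separate the two.

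**The growth curves adjust for baseline.** They remove a constant difference between teams. They do not remove differential replacement, and the planned cross-sectional tests do not use that protection.

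**The size rests on assumed inputs.** Correct. Neither the shift g nor its direction comes from the plan, and the ICC is borrowed.

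**Wider readings that the text does not support.**
- *Two years of differing exposure.* Coaching and ECHO run during the 12-month intervention period; the second year is for sustainability.
- *ECHO contrasts equally exposed.* The commitment asked of the Change Team differs by coaching dose, while ECHO adds calls for prescribers only.
- *Attitudes as a mediator.* Section 10 does not list them, and Table 2 places them under Adoption.

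**Conclusion.** The point holds as a gap in the plan. Site leaders select the Staff Survey respondents, no step fixes the selection before the arm is disclosed, and about 36% to 40% of month-24 respondents would be post-baseline joiners under the plan's turnover figure with leavers drawn at random or from original members. The models cannot distinguish a change in people from a change in the organization.

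The exposed comparisons are High- versus Low-Dose differences in Climate-Stress and staff attitudes, and in ORIC and Program Sustainability to the extent that these come from the Staff Survey. Section 6, Table 2 and section 8 must be reconciled on that. The mediation analyses using ORIC, Climate-Stress and Sustainability inherit the problem.

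A month-24 type I error of about 10% to 66% shows what is possible for assumed shifts of 0.25 to 0.8 SD; it is not a forecast. A reader might infer that the primary aim is compromised. It is not: Reach comes from monthly tracking or state data. The fidelity scales come from the Organizational Survey and also lie outside the point.

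**What to change.** 1. Have each site file its named Change Leader and Change Team list with the signed MOU, before its arm is disclosed, and say so in sections 4 and 6.
2. Keep all current respondents as the main staff analysis. Flag each person as original roster or later joiner, and add a respondent random effect to the models in section 10.
3. Report an original-roster analysis as a sensitivity analysis. It should not become the main one, because staying on the team is a post-randomization event that may itself depend on the arm.
4. Reconcile section 6, Table 2 and section 8 on which survey supplies ORIC and Program Sustainability.

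The cost is one administrative step before disclosure, one data flag and one extra model term. Some rosters may be out of date by a site's staggered start. The sensitivity analysis describes stayers only and is less precise, with a detectable difference of about 0.42 to 0.43 SD at month 24 against 0.37 SD with all respondents.
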